1.0 PROTOCOL SUMMARY AND/OR SCHEMA

This is a single-center, open-label phase II study of the combination of tafasitamab and lenalidomide in relapsed or refractory (R/R) mantle cell lymphoma (MCL) who have received previous treatment with a Bruton's tyrosine kinase inhibitor (BTKi). The study aims to evaluate the efficacy of the combination therapy. The primary endpoint will be objective response rate (ORR) to tafasitamab and lenalidomide, and will be evaluated when all patients have completed 12 cycles of treatment or at treatment discontinuation, whichever comes first.

Patients will be enrolled to receive tafasitamab via IV infusion and self-administer lenalidomide orally according to the treatment schema below, for a maximum of 36 cycles (3 years). In the first stage of the Simon 2-stage design, a total of 19 patients will accrue. If 6 or fewer have objective response, the trial will close due to a lack of efficacy; otherwise, an additional 20 patients will accrue. If at the end of the study, 17 or more out of 39 have an objective response, the trial will be considered promising for future development.

[figure not shown]
The anticipated accrual rate for this study is 1 to 2 patients per month, and the trial will continue through three years after the last accrued patient.

2.0 OBJECTIVES AND SCIENTIFIC AIMS

2.1 Primary objective

The primary objective of this study is to assess the ORR, defined as the percent of patients (relative to the total number considered evaluable as in 13.2) who achieve complete response (CR) or partial response (PR) according to the 2014 Lugano response criteria for non-Hodgkin lymphoma (NHL), to the combination of tafasitamab and lenalidomide in patients with R/R MCL who have experienced failure of or intolerance to past treatment with BTKi.^{1,2}

Figure 1: Treatment schema

2.2 Secondary objectives

- 2.2.1** To determine disease control rate (DCR), defined as the percent of patients (relative to the total number evaluable) who achieve CR, PR, or stable disease (SD) at the time of ORR assessment.
- 2.2.2** To estimate DOR, defined as the time from achievement of PR or CR to progression of disease (POD) according to Lugano criteria.^{1,2}
- 2.2.3** To estimate PFS, defined as the time from initiation of study treatment to the earlier of POD or death from any cause.
- 2.2.4** To estimate OS, defined as the time from initiation of study treatment to death from any cause.
- 2.2.5** To estimate TTP, defined as the time from initiation of study treatment to POD or death from MCL.
- 2.2.6** To describe the safety of the combination of tafasitamab and lenalidomide in patients with R/R MCL, defined as the incidence and severity (according to National Cancer Institute Common Terminology Criteria for Adverse Events (CTCAE) version 5.0).

2.3 Exploratory objectives

- 2.3.1** To assess the rate of conversion to undetectable minimal residual disease (MRD) by immunoglobulin gene next-generation sequencing (NGS) relative to baseline at 3, 6, and 12 months post initiation of study treatment; MRD will also be assessed at POD.
- 2.3.2** To characterize clonal evolution using circulating tumor DNA (ctDNA) in peripheral blood via high-depth targeted genomic sequencing at baseline, at 3, 6, and 12 months post initiation of study treatment, and at POD.
- 2.3.3** To evaluate effects of study treatment on:
 - Antitumor immune response (via surface protein expression, RNA expression, and variable, diversity, and joining (V(D)J) gene segment recombination of peripheral mononuclear cells (PBMCs)) relative to baseline at 3, 6, and 12 months post initiation of study treatment, and at POD.
 - MCL-driven immunosuppression in the tumor microenvironment (via flow cytometry enumeration of lymphocyte subsets in tumor biopsy samples) relative to baseline between days 21-28 of cycle 1, and at POD.

3.0 BACKGROUND AND RATIONALE

R/R MCL

MCL is an uncommon B-cell NHL comprising approximately 6-8% of all NHL diagnoses.^{3,4} MCL is more common in men than women, presents at a median age of 68 years, and is usually in an advanced stage at diagnosis, with bone marrow and the gastrointestinal tract being common extranodal sites of involvement.⁵ Despite improvement in overall survival of MCL with intensive frontline chemotherapy, it remains an incurable disease and most patients are destined to relapse after initial therapy.⁶ After relapse, MCL is more challenging to treat and is associated with progressively shorter remission durations after each subsequent line of therapy, resistance to traditional cytotoxic chemotherapy, and limited survival.⁷ The therapeutic landscape in MCL is rapidly evolving, and a number of biologically targeted therapies, such as lenalidomide, the Bruton's tyrosine kinase inhibitors (BTKis; ibrutinib, acalabrutinib, and zanubrutinib), and venetoclax, have demonstrated promising efficacy in the R/R setting.^{8,12} However, after failure of BTKi therapy, outcomes are generally poor for patients with R/R MCL, with median OS of 5.8 months.¹³

Recently, there was a promising therapeutic advance for R/R MCL with the FDA approval of brexucabtagene autoleucel, an anti-CD19 chimeric antigen receptor T-cell (CAR-T) therapy with an associated 93% ORR, including 67% with CR.¹⁴ Unfortunately, some patients may be ineligible for CAR-T, and others may face access constraints and logistical challenges given the need for referral to a specialized treatment center and the complexities associated with leukapheresis and manufacturing of the CAR-T product. In addition, this approach is associated with a high rate of adverse events (AEs), including grade 3 or higher cytokine release syndrome and neurologic events in 15% and 31% of patients, respectively. There remains a need for additional therapeutic options after BTKi failure, particularly in patients with R/R MCL with advanced age and multiple comorbidities.

Lenalidomide in MCL

Lenalidomide is an oral immunomodulatory imide drug (IMiD) with multiple immune-mediated and anti-angiogenic antitumor effects. Lenalidomide has been demonstrated to impede angiogenesis through inhibition of bFGF, VEGF, and TNF- α -induced endothelial cell migration, due at least in part to inhibition of Akt phosphorylation response to bFGF.¹⁵ Its myriad immunomodulatory effects include stimulation of T-cell proliferation, production of IL-2, IL-10, and IFNy, inhibition of IL-1 and IL6, and modulation of IL-12 production.¹⁶ Lenalidomide produces direct cytotoxicity in some hematologic malignancies through binding of cereblon, a component of the E3 ubiquitin ligase complex and thereby modulating protein ubiquitination and degradation.^{17,18} In MCL, lenalidomide's activity appears to be primarily mediated through expansion of CD56+ CD15+ NK cells and increased immune synapse formation, promoting NK cell-mediated cytotoxicity in the tumor microenvironment.¹⁹

Several studies demonstrated promising activity of single-agent lenalidomide as well as the combination of lenalidomide and the CD20 monoclonal antibody rituximab for treatment of

R/R MCL. In a subset of 57 patients with R/R MCL in the phase II NHL-003 study, lenalidomide 25mg daily was associated with an ORR of 35% with a median duration of response of 16.3 months after median follow-up of approximately 20 months.²⁰ In the larger international, multicenter phase II EMERGE study in patients with R/R MCL following bortezomib, single-agent lenalidomide produced an ORR of 28% (7.5% CR/unconfirmed CR (CRu)), with a similar median duration of response of 16.6 months.⁹ This study led to FDA approval of lenalidomide in patients with R/R MCL after at least two prior therapies, one of which included bortezomib. In a phase 1/11 trial of lenalidomide with rituximab, the combination was well-tolerated and produced an improved ORR of 57% (36% CR/CRu).²¹ The maximum tolerated dose of lenalidomide identified in the phase I portion of this trial was 20mg daily. One patient who received lenalidomide 25mg daily developed a grade 4 non-neutropenic infection and died.

After BTKis were established as a standard second-line treatment option for R/R MCL, there was interest in defining outcomes associated with lenalidomide-based therapy after BTKi failure or intolerance. This was evaluated in the retrospective MCL-004 study of a cohort of 58 patients with R/R MCL (13 treated with lenalidomide monotherapy, 11 with lenalidomide and rituximab, and 34 with other lenalidomide combinations).²² Patients had received median four prior lines of therapy (range 1-13), with an ORR of 29% (14% CR) and median duration of treatment of 8.4 weeks. The median DOR for responders was 20 weeks.

Tafasitamab in B-ce/1 NHL

Tafasitamab (MOR00208, previously XmAb5574) is an Fe-engineered, humanized monoclonal antibody that binds to the human B-cell surface antigen CD19.²³ CD19 is broadly expressed across the B-lymphocyte lineage, including in B-cell malignancies, but not by hematological stem cells. Tafasitamab produces significantly higher tumor cytotoxicity compared to the parental, non-engineered, murine 4G7 CD19 antibody. Tafasitamab has increased affinity for Fey receptors through the introduction of two amino acid modifications within the Fe region. Tafasitamab is associated with antibody-dependent cellular cytotoxicity (ADCC), antibody-dependent cellular phagocytosis, and exerts direct cytotoxicity. Preclinical studies indicate potent in vitro and in vivo activity of tafasitamab in lymphoma and leukemia models.^{23,24}

Tafasitamab was tested in a phase IIa study in B-cell NHL, including diffuse large B-cell lymphoma (DLBCL), follicular lymphoma (FL), other indolent NHL, and MCL.²⁵ Patients received tafasitamab 12mg/kg IV once weekly for 8 weeks, with those achieving at least SD eligible to continue treatment for an additional 4 weeks. Patients who achieved PR or CR after 12 weeks could receive further extended treatment every 2 or 4 weeks until POD. The primary endpoint of this study was ORR. Ninety-two patients were enrolled: 35 patients with DLBCL, 34 with FL, 11 with other indolent NHL, and 12 with MCL. Responses were observed among patients with DLBCL, FL, and other indolent NHL (ORR 26%, 29%, and 27%, respectively), including several durable responses. Among patients with MCL, there were no responders; however, six patients (50%) achieved SD, while five (42%) progressed and one

was not evaluable. This experience is in keeping with the poor activity rituximab monotherapy, which functions via similar mechanisms, in patients with untreated or R/R MCL.²⁶

Tafasitamab and lenalidomide

It was hypothesized that modulation of immune effector cells by lenalidomide would enhance NK cell-mediated ADCC exerted by tafasitamab, thereby resulting in therapeutic synergy when used in combination. Furthermore, given that prior rituximab exposure in patients with R/R DLBCL may result in down-regulated expression and/or internalization of CD20, it was postulated that targeting the conserved surface antigen CD19 with tafasitamab may overcome rituximab-related resistance and improve outcomes in the R/R setting.^{27,28} The combination of tafasitamab and lenalidomide was evaluated in 80 patients with R/R DLBCL in the single-arm phase II L-MIND study.²⁹ Patients received treatment for up to 12 cycles of 28 days each. In cycles 1 through 3, patients received tafasitamab intravenously on days 1, 8, 15, and 22, with an additional loading dose administered on day 4 of cycle 1. From cycle 4 onward, patients received tafasitamab on days 1 and 15. Patients self-administered lenalidomide 25mg orally once daily on days 1 through 21 of each cycle, with stepwise dose reduction if not tolerated. At median follow-up of 13.2 months, 48 patients (60%) achieved response (43% CR, 18% PR). The most common treatment-related AEs were hematologic, including neutropenia and thrombocytopenia. Given the promising efficacy and tolerability of this novel combination, tafasitamab and lenalidomide received accelerated FDA approval for use in transplant-ineligible patients with R/R DLBCL in August 2020.

Given the strong biologic and clinical rationale for therapeutic synergy of tafasitamab and lenalidomide in B-cell NHL, we hypothesize that this combination will improve upon outcomes associated with lenalidomide-based therapy for MCL in the post-BTKi R/R setting. Patients with R/R MCL typically receive rituximab and may develop resistance to it. Targeting CD19 is a clearly efficacious strategy in MCL given the high response rates associated with CD19-directed CAR-T therapy. However, this approach can be associated with significant toxicity and challenging to access, particularly in elderly patients who often present with comorbidities. Combination therapy with tafasitamab and lenalidomide may offer improved outcomes with minimal toxicity, potentially fulfilling an unmet need in a population with few acceptable treatment options.

3.1 Correlative Studies

In the course of this research it is possible that some patients whose tumors are analyzed through investigational "next-generation" profiling in a research (non-CUA) environment will be found to have somatic or germline mutations in genes that are known to be associated with an increased risk of cancer or other diseases. It will be stated in the consent that the participants will not receive any specific results from research tests. The consent will tell participants that if they wish to have genetic testing done for personal reasons than they should make an appointment with the MSK Clinical Genetics Service.

If in the course of this research a research finding is obtained that, in the opinion of the investigator, may be critical to the preventive care of the participant or their family, the investigator can communicate that finding to the IRB Genomic Advisory Panel (GAP). The finding will be reviewed by the GAP to determine whether the incidental finding should be discussed with the participant. For MSK, in the event that the GAP determines that the finding should be discussed with the participant, and the participant has consented to be re-contacted, then the treating/consenting physician shall be contacted by the panel and asked to refer the participant to the Clinical Genetics Service for further discussion of the research finding.

The following information must be provided to GAP for review:

- Participant Name/MRN #
- Type of Biospecimen (tissue, blood, saliva)
- Incidental Finding
- Collection Protocol #
- Contact: [contact]

1. Effects of lenalidomide and tafasitamab on the peripheral immune system

Lenalidomide has been shown to enhance the anti-tumor immune function of both T-cells and NK cells. The reinvigoration of dysfunctional immune cells can be monitored in the blood using multiparametric flow cytometry, including assessment of activation state, proliferative capacity, and expression of exhaustion markers. We hypothesize that patients responding to tafasitamab and lenalidomide will exhibit an increase in both the activation state and proliferative capacity of CD3+ T-cells and NK cells, while non-responding or progressing patients will exhibit an increase in exhaustion markers. To test these hypotheses, multiparametric flow cytometry will be performed in the laboratory of [name]. The [name] laboratory has already published several papers in using deep immune profiling and high-dimensional flow cytometry analysis of peripheral blood mononuclear cells in hematologic malignancy patients with COVID-19 infection (Bange, Han et al, *Nat Med* 2021, Lyudovsky, Han, Qualls et al *Cancer Cell*, in press).

These analyses will include:

- Assessment of CD4+ and CD8+ T-cell differentiation state (CD45RA, CD27, CCR?, TCF-1, T-bet, Eames, FoxP3)
- Activation state of T-cells and NK cells (CD38hi/HLA-DRhi)
- Proliferative capacity of T-cells and NK cells (Ki-67hi)
- Exhaustion state of T-cells and NK cells (expression of PD-1, LAG-3, Tim-3, and CTLA-4)

We have hypothesized that the combination of tafasitamab and lenalidomide will facilitate antigen spreading leading to a polyclonal, polyfunctional T and NK cell anti-tumor immune response. To determine whether tafasitamab and lenalidomide promote a diversified immune response, we will perform unbiased profiling of both PBMCs and, when possible, single-cell suspensions from primary tumor samples using CITE-Seq technology, in which surface protein and RNA expression are interrogated in single-cells. This will allow for clone-specific tracking of T and NK cell evolution in response to therapy. We plan to collect peripheral blood mononuclear cells (PBMCs) at day 1 of cycles 1, 2, and 3, and at progression. In addition, when possible, we will perform parallel studies on CD45+ cells from primary tumor biopsies (either lymph node, tumor, or bone marrow, if known involvement), which will be performed pre-treatment and at disease progression. There will also be an optional tumor biopsy performed between C1D22 and C1D28 of treatment. These studies will be performed in collaboration with MSKCC's Single Cell Research Institute (SCRI).

2. Effect of lenalidomide and tafasitamab on the tumor microenvironment.

The tumor microenvironment is known to suppress the effector function of tumor-infiltrating T- and NK-cells across multiple cancer subtypes. We therefore hypothesize that the composition of the local MCL microenvironment will be a key determinant of response to tafasitamab and lenalidomide. We will use two parallel strategies to test this hypothesis. First, single-cell suspensions will be generated from core biopsies and analyzed for intratumoral immune cell composition (including but not limited to T, B, NK cell, macrophages, and dendritic cells) via multi-parametric flow cytometry performed on fresh biopsy samples by MSKCC's Hematopathology service. Should additional tumor biopsy samples be available, we will analyze the composition of the tumor microenvironment both at baseline and in response to therapy using CITE-Seq technology identical to that described above. If we see evidence of increased immune cell recruitment, we will pursue additional downstream assays such as multiplexed ion beam imaging (MIBI) in collaboration with the Immune Monitoring Facility. We will collect biopsy (either fine needle aspiration or core needle biopsy of lymph node or bone marrow) at baseline and at time of progression. There will also be an optional biopsy (either fine needle aspiration or core needle biopsy of lymph node or bone marrow) performed between C1D22 and C1D28 of treatment.

3. Mechanism of synergy between lenalidomide and tafasitamab and mechanisms of resistance to combination therapy

The mechanism by which lenalidomide alters immune function was recently described; lenalidomide binds and redirects cereblon, resulting in E3-dependent ubiquitylation and degradation of several proteins including the Ikaros family of transcription factors (including Ikaros and Aiolos). These transcription factors are expressed in most lymphocyte subsets, and therefore the mechanism by which lenalidomide alters both lymphoma cell and infiltrating immune cell function remains poorly characterized, particularly in mantle cell lymphoma. To interrogate the epigenetic effects of lenalidomide, we will perform single-cell ATAC-sequencing and paired CITE-sequencing of bone marrow samples isolated from patients both prior to initiation of therapy and at disease progression. The goal of this analysis will be

to determine whether progression of disease in patients occurs because a) activity of Ikaros family transcription factors is restored, or b) immune suppression persists in the absence of recurrent Ikaros-dependent transcriptional activation.

4. Minimal residual disease (MRD)

MRD assessment can further refine response assessment in MCL and provides prognostic information in MCL [33558202]. In this study, we will perform MRD assessment using a next generation immunosequencing (IS) MRD assay (Adaptive Biotechnologies, Seattle, WA). This IS MRD assay leverages multiplex PCR followed by NGS to identify and track rearrangements of IgH, V-J, D-J and IgK/L loci and translocations in Bcl1/2-IgH. Peripheral blood will be collected at screening, day 1 of cycles 3, 7, and 13, and at end of treatment for MRD analysis, and evaluated for association with progression-free survival.

5. Clonal evolution in MCL.

Dynamic molecular monitoring in MCL patients treated with biologically targeted agents, such as ibrutinib and venetoclax, have revealed mutations that mediate therapeutic resistance [30455436]. In this study, we aim to characterize the clonal evolution of MCL in serial patient samples on treatment with tafasitamab and lenalidomide. Patients will have ctDNA in peripheral blood collected and banked for genomic testing by high-depth targeted sequencing pretreatment and serially during therapy, in order to study the effect of protocol therapy on clonal composition of MCL and assess whether genetic alterations arise that are associated with resistance. An MSK platform for assessment of circulating tumor DNA in peripheral blood specimens will be utilized.

6. Tumor molecular profiling and prognosis

Molecular analysis of diagnostic tumor samples obtained during screening with paired normal tissue (saliva or nails) will be analyzed using the MSK IMPACT platform under IRB protocol 12-245. Genomic alterations in MCL will be analyzed for associations with key clinical outcomes including PFS, ORR, and OS.

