4.2 Intervention

Patients will receive treatment with intravenous tafasitamab and oral lenalidomide for up to 12 cycles. Each cycle is 28 days in length. Lenalidomide will be self-administered at a dose of 20mg daily days 1-21 of cycles 1 through 12. During the first cycle, tafasitamab will be administered on days 1, 4, 8, 15, and 22. During cycles 2 and 3, tafasitamab will be administered weekly on days 1, 8, 15, and 22. During cycles 4 through 12, tafasitamab will be administered every other week on days 1 and 15. Upon earliest of completion of cycle 12 or EOT, patients will undergo radiologic evaluation of response. Patients who achieve SD, PR, or CR at completion of cycle 12 will continue tafasitamab maintenance therapy on day 1 of each cycle until the earliest of POD or 36 cycles (inclusive of the first 12 cycles).

Figure 1: Treatment schema

*One cycle = 28 days

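### Section 3.1 does not schedule the PBMC samples at 3, 6 and 12 months that objective 2.3.3 needs, and its first on-treatment MRD draw falls at about 2 months, not 3

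*Combined protocol and SAP*

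**What the plan says.** **Objectives (Section 2.3).** Conversion to undetectable MRD (2.3.1) is to be assessed "relative to baseline at 3, 6, and 12 months post initiation of study treatment; MRD will also be assessed at POD". Peripheral immune response in PBMCs (2.3.3) is to be assessed "relative to baseline at 3, 6, and 12 months post initiation of study treatment, and at POD". The ctDNA objective (2.3.2) uses the same months: "at baseline, at 3, 6, and 12 months post initiation of study treatment, and at POD".

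**Collection (Section 3.1).** For PBMCs: "We plan to collect peripheral blood mononuclear cells (PBMCs) at day 1 of cycles 1, 2, and 3, and at progression". For MRD: "Peripheral blood will be collected at screening, day 1 of cycles 3, 7, and 13, and at end of treatment for MRD analysis". For ctDNA no visits are named, only "high-depth targeted sequencing pretreatment and serially during therapy".

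**Which section governs.** Section 14.0 refers the reader to Section 3.1 for the exploratory objectives, their designs and their analytic approaches. Section 11.2 sends MRD, ctDNA and PBMC collection to Table 11-1 and to a lab manual. Table 11-1 has a single research-blood row that is not split by assay.

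**Cycle length (Section 4.2).** "Each cycle is 28 days in length".

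**The concern.** The objectives are written in months and the collection plan in cycles, and the two do not meet.

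- **PBMCs.** If staff follow Section 3.1, a patient who has not progressed gives no PBMC sample after cycle 3 day 1. The immune-response objective then has no data at any of its three on-treatment time points. Blood that was not drawn cannot be recovered later.
- **MRD, first draw.** A conversion rate reported as the 3-month rate would describe an earlier time. Section 14.0 also plans a log-rank test of MRD against PFS, and its reading depends on when MRD was measured.
- **MRD, last draw.** Progression and end of treatment are different events for a patient who stops for toxicity or who completes 36 cycles without progressing. The two sections therefore ask for different final samples in those patients.

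**Working it through.** No figure in the plan needs reproducing. The check is calendar arithmetic plus a side-by-side reading.

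**Inputs.** Cycle length 28 days (Section 4.2). Objective times 3, 6 and 12 months (Section 2.3). Collection visits from Section 3.1. One calendar month = 365.25 / 12 = 30.44 days. As an alternative, one cycle = one month, because Section 1.0 equates 36 cycles with three years.

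**Formula.** Days from treatment start to day 1 of cycle k = (k − 1) × 28. Calendar months = days / 30.44. Times are nominal, with no delayed cycle starts.

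| Visit | Days after start | Calendar months | If one cycle = one month |
|---|---|---|---|
| C2D1 | 28 | 0.92 | 1 |
| C3D1 | 56 | 1.84 | 2 |
| C4D1 | 84 | 2.76 | 3 |
| C7D1 | 168 | 5.52 | 6 |
| C13D1 | 336 | 11.04 | 12 |

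**Set against the objectives.**

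| Objective time | MRD draw in 3.1 | PBMC draw in 3.1 |
|---|---|---|
| Baseline | Screening | C1D1 |
| 3 months | C3D1 (1.84 calendar months; 2 cycles) | None (last fixed draw is C3D1) |
| 6 months | C7D1 (5.52; 6 cycles) | None |
| 12 months | C13D1 (11.04; 12 cycles) | None |
| Progression | End of treatment instead | Progression |

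**Size of the first MRD gap.** Three calendar months are 91.3 days, so C3D1 is 91.3 − 56 = 35.3 days early, or 35.3 / 91.3 = 39%. On the cycle-as-month reading it is one cycle early: 84 − 56 = 28 days, or 28 / 84 = 33%. C3D1 is not 3 months on either reading.

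**The later MRD draws.** By calendar, C7D1 is 182.6 − 168 = 14.6 days early and C13D1 is 365.25 − 336 = 29.25 days early. On the cycle-as-month reading both match exactly. The calendar yardstick should not be used to fault C3D1 while C13D1 is accepted; the fault at C3D1 rests on its failing both yardsticks.

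**The case against.** **Table 11-1 may hold the missing draws.** This is the strongest objection, because Section 11.2 makes that table and the lab manual the operational schedule. In the available copy the table cannot settle the matter. Its cycle 4 to end-of-treatment part shows one research-blood mark, although Section 3.1 alone requires MRD blood at C7D1, C13D1 and end of treatment. The PET and CT rows there are empty, although Section 4.2 requires imaging at the end of cycle 12. Marks have evidently been lost or shifted, so an absent mark is no evidence of an absent draw. A reader might infer that the trial plans no 6- or 12-month PBMC sample at all. The documents do not support that; the gap is shown for Section 3.1 only. This part of the objection stands, but an intact table would still leave Sections 2.3 and 3.1 in conflict.

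**A cycle is shorthand for a month.** This stands for C7D1 and C13D1. A reader might infer that the whole MRD schedule is wrong, but the material timing mismatch is confined to the first on-treatment draw. The shorthand rescues neither C3D1 nor the PBMC schedule.

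**ctDNA.** A reader might infer the same contradiction there. None is shown: Section 3.1 names no ctDNA visits, so there is nothing for the months in 2.3.2 to conflict with.

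**The objectives are exploratory and mostly descriptive.** True, and it limits the weight of the point. An MRD rate at C3D1 is interpretable if labelled as such, and the planned MRD–PFS test names no month. It does not remove the need to decide which samples to draw before the visits pass.

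**Conclusion.** The point holds as an inconsistency between sections. Section 3.1 delivers none of the 3-, 6- and 12-month PBMC samples in objective 2.3.3. Its first on-treatment MRD draw is 28 to 35 days short of 3 months, depending on the month convention. The final MRD sample is tied to progression in one section and to end of treatment in the other.

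This rests on the wording of Sections 2.3 and 3.1, on 28-day cycles without delays, and on Section 14.0 pointing to Section 3.1 for the exploratory designs. What would actually be drawn remains open until the source Table 11-1 and the lab manual are checked.

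A reader might also infer damage to the main efficacy result. There is none: ORR, the two-stage decision rule, the secondary endpoints and the safety analysis use none of these samples. The correction is worth making because it is cheap now and impossible once the visits have passed.

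**What to change.** Check the source Table 11-1 and the lab manual first. Then state one schedule per assay, in cycles and with visit windows, and use it in Section 2.3, Section 3.1, Table 11-1 and the lab manual.

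- **MRD:** either move the C3D1 draw to C4D1, or relabel the objective as cycle 3 day 1. State whether the last sample is at progression, at end of treatment, or both.
- **PBMCs:** either add tubes at C4D1, C7D1 and C13D1, or rewrite 2.3.3 to the C2D1, C3D1 and progression times that Section 3.1 lists. The investigators should choose according to whether early or sustained immune change is the question.
- **ctDNA:** name the visits in the same schedule, for consistency.
- **Table 11-1:** split the research-blood row by assay.

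**Cost.** Wording changes to the protocol and lab manual. Adding PBMC draws means a few extra tubes and their processing, but no new visits: under Section 10.1 patients on treatment already attend day 1 of cycles 4 and 7 for tafasitamab, and day 1 of cycle 13 if they have stable disease or better. Rewriting 2.3.3 costs no samples but narrows the objective to the first two months and progression.
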